15 APR 2016

Trial Protocol Proprietary confidential information © 2016 Boehringer Ingelheim International GmbH or one or more of its affiliated companies

Page 94 of 137

# Further information

The Respimat® inhaler must not be disassembled after inserting the cartridge and replacing the clear base.

Do not touch the piercing element inside the base.

Keep out of the reach and sight of children.

Do not freeze.

Boehringer Ingelheim Pharma GmbH & Co. KG D - 55216 Ingelheim, Germany

**(€** 0123 HI-Master-Version-06-tiotropium+olodaterol-combination-Respimat-20140516

Boehringer Ingelheim

c03207491-01

15 APR 2016 BI Trial No.: 1237.28

Trial Protocol Proprietary confidential information © 2016 Boehringer Ingelheim International GmbH or one or more of its affiliated companies

Page 95 of 137

#### 10.2 RETURN OF INHALERS/CARTRIDGES

# Return of Malfunctioning Respimat® Inhalers

Respirat® inhalers, with the used cartridge in situ, that appeared to malfunction, will be returned to BI as soon as possible. Procedures for this return, including name, address and contact person are provided in the ISF.

c03207491-01 Trial Protocol Page 96 of 137

Proprietary confidential information © 2016 Boehringer Ingelheim International GmbH or one or more of its affiliated companies

# 10.3 ADDITIONAL INFORMATION REGARDING IN/EX CRITERIA

Reversibility testing [P05-12782]

At the screening visit (visit 1), following the completion of three acceptable pre-bronchodilator forced expiratory manoeuvres, salbutamol (albuterol) will be administered to each patient in order to document the degree of reversibility. Immediately after (within 10 min) pre-bronchodilator forced expiratory manoeuvres and after a gentle and incomplete expiration, a dose of 100 μg of salbutamol (albuterol) is inhaled in one breath to TLC. The breath is then held for 5–10s before the patient exhales. Four separate doses (total dose 400 μg) are delivered at approximately 30-second intervals (this dose ensures that the response is high on the salbutamol (albuterol) dose—response curve). Three additional, acceptable post-bronchodilator forced expiratory manoeuvre tests are recorded ≥10 min and up to 15 min later after the last dose of salbutamol (albuterol) is inhaled. !"# \$%&)\*%+,"%-.0'%\*1#0&2\*#1#+'&12&' 1##' ""# .+,/2&.%+\*.'#\*.0 &\$#,.3.#-.+ &#,'.%+45465

The spirometers and their use, including daily calibration, must meet American Thoracic Society (ATS)/ European Respiratory Society (ERS) criteria.

Calculation of predicted normal values according to ECSC [R94-1408]

For height measured in inches

Males:  $FEV_1$  predicted (L) = 4.30 x [height (inches)/39.37] - 0.029 x [age (yrs)] - 2.49

Females:  $FEV_1$  predicted (L) = 3.95 x [height (inches)/39.37] - 0.025 x [age (yrs)] - 2.60

For height measured in meters

Males:  $FEV_1$  predicted (L) = 4.30 x [height (m)] - 0.029 x [age (yrs)] - 2.49

Females:  $FEV_1$  predicted (L) = 3.95 x [height (m)] - 0.025 x [age (yrs)] - 2.60

Ethnic adjustments may be made as appropriate as per ATS/ERS recommendations [P05-12646, R94-1408].

Calculation of number of pack years

Pack years =  $\frac{\text{Number of cigarettes/day}}{20}$  X years of smoking

BI Trial No.: 1237.28

c03207491-01 Trial Protocol Page 97 of 137

Proprietary confidential information © 2016 Boehringer Ingelheim International GmbH or one or more of its affiliated companies

### 10.4 EXERCISE TESTING – ISWT AND 3MIN CSST

To supplement the information on exercise testing using the ISWT and 3min CSST described in this chapter, a Manual of Procedures (MOP) has been developed. More detailed information on the procedure, on staffing, site and equipment requirements, patient preparation, IC measurements, and calculations etc. can be found in this MOP, which is filed in the ISF.

# 10.4.1 General considerations for exercise testing

# Exercise performance variability

A number of physiological and psychological factors are known to affect exercise performance. Lack of attention to controlling these extraneous factors may result in an unacceptable degree of variability in exercise performance. As such, certain requirements have been put in place to reduce exercise performance variability:

# Physiological:

Pre-exercise diet: Patients are to be encouraged to eat breakfast before coming to the clinic. However, patients should not eat within 2 hours of exercise tests.

- Hydration state: Patients are to be encouraged to maintain an adequate hydration state during the morning of the exercise tests (i.e., drink lots of water).
- Environmental conditions (temperature, humidity): Temperature and humidity should be controlled within the laboratory at comfortable levels, and should be recorded each testing day.

### Previous exercise:

- Fatigue: Patients should be encouraged to stay well-rested and to refrain from any strenuous, fatiguing or exhausting activities (e.g., walking up hills, walking up many flights of stairs, running, cycling, shovelling snow, strenuous household chores) on the morning of exercise tests.
- Delayed onset muscular soreness (DOMS): Very strenuous, heavy type of activities, especially activities to which the patient is unaccustomed, can lead to muscle soreness 24-48 hours after the activity. Patients should be encouraged to refrain from any type of heavy lifting, exhaustive digging in the garden etc., for 2-3 days prior to each clinic visit, especially if the patient has not performed these activities recently.

### Psychological:

• External motivational cues: Motivational cues provided to the patient can have profound effects on exercise performance. It is imperative that external motivational cues are controlled across patients and across sites.

Boehringer Ingelheim BI Trial No.: 1237.28

c03207491-01

15 APR 2016

Trial Protocol Proprietary confidential information © 2016 Boehringer Ingelheim International GmbH or one or more of its affiliated companies

Time of exercise: No visual cues regarding the time of exercise should be provided to the patient. The patient's watch should be removed prior to exercise, and all other timekeeping devices (e.g., trial staff watches, wall clocks, stopwatch etc.) should be kept away from the patient's view.

Page 98 of 137

- Verbal encouragement: During exercise testing, the wording and intensity of verbal encouragement provided to the patient will be standardized, and will preferably only be provided by one member of the trial team, who is blinded to the results of the lung function tests. Appropriate positive words should be used to encourage the patient to continue walking. The tone of the encouragement should be enthusiastic and supportive, but not overbearing, overly loud or coercive in nature. Examples would be "good work", "well done", "excellent job so far" and "keep up the good work". Reinforcement could also consist of "that's a good walking rate" or, if the walking rate is dropping, "keep up the walking rate - that's great".
- Familiarity with surroundings: Trial staff should allow as much time as necessary for the patient to become comfortable with the laboratory surroundings.
- Distractions: During the exercise tests, access to the laboratory should be restricted to trial staff as much as possible. The noise level in the laboratory should be kept to a minimum, except for those sounds specifically related to the conduct of the test. This will ensure that the patient is able to concentrate on the task at hand, and will also ensure that the patient is attentive to the verbal encouragement provided by the designated member of the trial team.
- Comfort with equipment: Patients should be appropriately dressed for exercise (e.g., shorts or track pants, gym shoes, T-shirt or sweat shirt), and trial staff should ensure that the patient is comfortable with the equipment prior to starting the exercise.
- Familiarity with test: Before starting exercise, a member of the trial team should make sure that the patient is completely familiar with the type of exercise that is to be performed; for the incremental test, patients should be told that during the test they will have to walk progressively faster. For the constant speed tests, patients should be told that the speed of walking will be constant throughout the test. It is important that the patient understands the difference between the incremental test and the constant speed tests.
- For the ISWT: It is extremely important that the patient understands that there is no specific time limit to the exercise test, and that the test will continue as long as the patient is able to. It must be stressed to the patient that the trial team will not stop the test unless there is concern for the patient's safety, or the patient is unable to maintain the required walking pace.

Boehringer Ingelheim
15 APR 2016
BI Trial No.: 1237.28

c03207491-01 Trial Protocol Page 99 of 137

Proprietary confidential information © 2016 Boehringer Ingelheim International GmbH or one or more of its affiliated companies

• Performance incentives: No external incentives for performance (i.e., rewards for performance) should be given to the patient, especially as the patient nears the point of limitation, but also prior to or at any time during the exercise.

# Heart rate and safety monitoring:

- Heart rate and oxygen saturation will be monitored during shuttle tests using a mobile pulse oximeter.
- Blood pressure will be determined before exercise, at end-exercise, five minutes after termination of exercise and when, for clinical reasons, it is required.

# Personnel qualifications:

- Exercise challenges should be conducted by adequately trained personnel with a basic knowledge of exercise physiology.
- Technicians familiar with normal and abnormal responses during exercise and trained in CPR should be present throughout the test.
- The supervising physician must be readily available to respond as needed. The degree of patient supervision should be increased if warranted by the clinical status of the patient.

# Safety issues:

Cardiac (bradyarrhythmias, ventricular tachycardia, myocardial infarction, heart failure, hypotension, and shock) and non-cardiac (musculoskeletal trauma, severe fatigue, dizziness, fainting, body aches) complications of exercise challenges have been reported. Consequently during the test, study personnel should be alert to any abnormal event.

Indications to stop the test must be clearly established and known by the personnel involved in testing.

# Symptoms such as:

- acute chest pain,
- sudden pallor,
- loss of co-ordination,
- mental confusion,
- extreme dyspnea.

If the exercise test has been stopped for one of these reasons, the patient should be monitored in the laboratory until signs / symptoms / ECG modifications have completely cleared. Full CPR equipment should be available in the laboratory. The patient will be withdrawn from the study.

BI Trial No.: 1237.28

c03207491-01 Trial Protocol Page 100 of 137

Proprietary confidential information © 2016 Boehringer Ingelheim International GmbH or one or more of its affiliated companies

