## Visits 4 and 7 Procedures and Observations

## First visit of each treatment period

Medication washout	Medication washout compliance for prohibited medications will be verified and visits may be rescheduled as appropriate (section 6.1)
Questionnaires	To be completed in the following order: CRQ-SAI (Appendix 10.10),

Boehringer Ingelheim BI Trial No.: 1237.28

Proprietary confidential information © 2016 Boehringer Ingelheim International GmbH or one or more of its affiliated companies c03207491-01

	CRQ-SAS (Appendix 10.9),
	To be performed prior to dosing and study procedures.
Adverse Events	All AEs experienced since the previous visit will be reviewed and documented.
Concomitant Therapy	Any changes in concomitant medications since the last visit will be reviewed and documented.
Inclusion / Exclusion Visit 4 only	To be reviewed.
Smoking Status	Will be recorded
Urine Pregnancy	Will be performed if needed.
Vital Signs	Blood pressure and pulse rate will be measured immediately before PFTs with the patient seated and rested for at least five minutes.
Spirometry	Baseline spirometry measurements will be performed between 7:00 and 10:00am and prior to exercise testing. Refer to FC .
	The 24-hour clock time of the last cigarette smoked during the 12 hours prior to the start of lung function measurements will be recorded.
3min CSST	To be performed prior to dosing at the speed selected at visit 2. Please refer to Appendix 10.4.1.
	
 
The following will be measured during 3min CSST (please refer to FC):
 
BORG measurements - at rest, 1, 2, 2.5 minutes during exercise and at 3 min or the end of exercise. Refer to Appendix 10.5 for further details.
 

	IC - at rest and at end of exercise using mobile cardiopulmonary exercise equipment. Refer to Appendix 10.7 for further details
Randomisation Call Visit 4 only	To be performed by calling IRT.

BI Trial No.: 1237.28

c03207491-01 Trial Protocol Page 69 of 137

Proprietary confidential information © 2016 Boehringer Ingelheim International GmbH or one or more of its affiliated companies

Assignment and dispensing of trial drug	Allocate the appropriate medication kits using IRT.  2 Respimat ® treatment boxes and 1reserve Respimat ® inhaler are assigned.

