### 10.4.2 Shuttle Test

Shuttle tests will be performed in all patients of this trial. Selection of sites is based on past experience with the test and/or the availability of suitable infrastructure and qualified personnel.

The shuttle test is performed on a flat, straight walking track, in a quiet treatment area that is at least 12 meters in length and approximately 2 meters wide, and clear of hospital traffic and obstacles. The standard instructions are given by trained site staff. Patients are required to walk, jog or run back and forth, in loops of 10 meters long. Cones are placed half a meter from the end, so they are 9 meters apart. The patient must keep pace with the pre-recorded auditory signal such that he/she completes a turn as each audio signal sounds.

[figure not shown]

Figure 10.4.2:1: Set up for the shuttle test

During the test oxygen saturation and heart rate will be monitored using a pulse oximeter (fingertip or ear lobe sensor). Patients will also wear mobile cardiopulmonary exercise equipment. A chair should be placed in the immediate surroundings of the track for the patient to rest before and at the end of the test.

For the ISWT at visit 1, the end of the test will be signaled

- a) by the patient, when he feels too breathless or fatigued to continue at the required speed.
- b) by the operator when the patient fails to keep up to auditory signals after repeated warnings and encouragements (patient is more than 0.5 meter from the cone at the beep) and is unable to catch up within 3 shuttles.
- c) when the patient is unable to continue safely (in the opinion of the supervising technician or physician).

For the 3min CSST, the end of the test will be signaled

- a) by the patient, when he feels too breathless or fatigued to continue at the required speed.
- b) by the operator when the three minutes of testing is completed.
- c) by the operator when the patient fails to keep up to auditory signals after repeated warnings and encouragements (patient is more than 0.5 meter from the cone at the beep) and is unable to catch up within 3 shuttles.
- d) when the patient is unable to continue safely (in the opinion of the supervising technician or physician).

Boehringer Ingelheim

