15 APR 2016
BI Trial No.: 1237.28

c03207491-01 Trial Protocol Page 101 of 137

Proprietary confidential information © 2016 Boehringer Ingelheim International GmbH or one or more of its affiliated companies

The test should also be interrupted when symptoms occur as described in the safety section above.

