6.3 PATIENT SETS ANALYSED

The following nested patient sets are defined:

- Randomised set (RS):

This patient set includes all patients who signed informed consent form and were also randomised, regardless whether the patient was treated with study medication or not.

- **Treated set (TS):**

This patient set is nested within RS and includes all patients who were dispensed study medication and were documented to have taken any dose of study medication. TS will be used for patient disposition, demographics and baseline disease characteristics, concomitant therapies, treatment compliance, treatment exposure and safety analyses (including AEs and vital signs).

- **Full analysis set (FAS):**

This patient set is nested within TS and includes patients who had baseline measurement and at least one post-baseline measurement for the primary endpoint. The FAS will be used for the efficacy analyses. Assignment to the FAS will be done after implementation of any data handling rules which set measurements to missing.

- **Per protocol set (PPS):**

This patient set is nested within FAS and includes only patients who had no important PVs which are specified to be excluded from the PPS ([Table 6.3: 1](#)). The final decision regarding which patients are excluded from PPS will be made at BRPM prior to data unblinding.

If the number of patients in PPS is less than 90% of the number of patients in FAS, the primary analysis for the primary endpoint will also be performed on the PPS as supportive analyses.

Table 6.3: 1 Patient sets analysed

Class of endpoint	Patient Sets		
	TS	FAS	PPS
Primary endpoint		primary analysis	supportive analysis*
Secondary endpoints		X	
Further endpoints		X	
Safety endpoints	X		
Demographic/baseline endpoints/exposure	X		

* Performed only when the number of patients in PPS is less than 90% of the number of patients in FAS as sensitivity analysis.

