6.6 HANDLING OF MISSING DATA AND OUTLIERS

As noted in the protocol, in general, missing data at a given visit will be imputed by the available data from the patient at that visit and completely missing visits will be handled through the statistical model.

Completely missing visits not due to worsening of study disease will not be imputed and will stay as missing, because such missing data are considered as randomly missing data and will be handled in the mixed model repeated measures model.

Completely missing visits due to the patient discontinuing due to worsening of study disease will be imputed with the least favourable prior visit during that period.

It could happen that a patient needed therapy for COPD symptoms at a clinic visit. This therapy was entered on the rescue medication electronic Case Report Form (eCRF). This may or may not be the rescue medication provided by Boehringer Ingelheim (BI). For purposes of the imputation rules this will be termed “rescue medication” regardless of whether or not it was BI-supplied rescue medication.

The following rules are used for exercise data:

In situations where the full 3-min of exercise was completed:

- Measurements of Borg breathing discomfort scale, [REDACTED] which are missing for the 3 minute time point will be imputed using the last non-missing observation during exercise (but not non-missing measurements at rest) for that visit.
- Measurements of Borg breathing discomfort scale, [REDACTED] which are missing for all other time points during exercise will not be imputed (i.e. left as missing).

In situations where exercise is terminated prematurely:

- Borg breathing discomfort [REDACTED] scores will be imputed from end-of-exercise value for all time points beyond the exercise termination (including the 3 minute time point).

[REDACTED]

In addition, the following rules apply:

[REDACTED]

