6.7 BASELINE, TIME WINDOWS AND CALCULATED VISITS

Period baseline

The period baseline is defined as the pre-dose measurement, performed prior to dosing on the first day of each period.

Patient baseline

The patient baseline is defined as the mean of non-missing period baselines for each patient.

Study baseline

For endpoints with only one baseline measurements prior to the first treatment period, this baseline will be called study baseline.

More specifically,

Baselines for Primary Endpoint

The primary endpoint is the change from baseline in intensity of breathlessness measured using the MBS-S at the end of the 3min Constant Speed Shuttle Test (CSST) after 6 weeks of treatment.

- Period baselines are measured at the end of the 3 min CSST at visits 4 and 7

Period Baselines for Secondary Endpoints

Change from baseline in Inspiratory Capacity (IC) measured prior to exercise, after 6 weeks of treatment.

- Period baselines are measured in resting IC (Omnia) prior to exercise at visits 4 and 7

Change from baseline in IC measured at the end of exercise, after 6 weeks of treatment

- Period baselines are measured in IC at the end of exercise at visits 4 and 7

Change from baseline in 1 hour post-dose FEV₁, after 6 weeks of treatment.

- Period baselines are measured in pre-dose FEV₁ at visits 4 and 7

Change from baseline in 1 hour post-dose FVC, after 6 weeks of treatment.

- Period baselines are measured in pre-dose FVC at visits 4 and 7

Change from baseline in intensity of Breathlessness (MBS-S) at 1min, 2min, and 2.5min during the 3min CSST after 6 weeks of treatment.

- Period baselines are measured at the corresponding time point during the 3 min CSST at visits 4 and 7

Change from baseline in Chronic Respiratory Questionnaire - Self Administered Individualized (CRQ-SAI) dyspnea domain score after 6 weeks of treatment.

- Period baselines are collected at visits 4 and 7

Change from baseline in Chronic Respiratory Questionnaire - Self Administered Standardized (CRQ-SAS) dyspnea domain score after 6 weeks of treatment.

- Period baselines are collected at visits 4 and 7

[REDACTED]

[REDACTED]

[REDACTED]

[REDACTED]

[REDACTED]

[REDACTED]

[REDACTED]

[REDACTED]

Time windows and calculated visits

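### If a shuttle test at visit 7 is stopped for extreme dyspnea, could SAP 6.6 turn a pre-dose score into a six-week result?

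*Protocol*

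**What the plan says.** Protocol Appendix 10.4.1 lists symptoms for which an exercise test is stopped, including extreme dyspnea, and then states: "The patient will be withdrawn from the study". Appendix 10.4.2 separately lists how the three-minute test can end. One way is "by the patient, when he feels too breathless or fatigued to continue at the required speed", with no withdrawal attached. After that list it adds: "The test should also be interrupted when symptoms occur as described in the safety section above".

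SAP 6.6 has two rules for a visit that is missing altogether. One reads "Completely missing visits not due to worsening of study disease will not be imputed and will stay as missing". The other covers visits lost to "the patient discontinuing due to worsening of study disease will be imputed with the least favourable prior visit during that period".

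The visit 7 test belongs to period 2 but precedes drug. Protocol 6.2.2 says of the test at visits 4 and 7: "To be performed prior to dosing at the speed selected at visit 2". SAP 6.7 says: "The period baseline is defined as the pre-dose measurement, performed prior to dosing on the first day of each period". Membership of the full analysis set is decided per patient: SAP 6.3 "includes patients who had baseline measurement and at least one post-baseline measurement for the primary endpoint". Visits 4 and 6 are therefore enough to keep a patient in.

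**The concern.** Two gaps seem to combine. First, the protocol does not say where ordinary breathlessness ends and extreme dyspnea begins. No anchor of the modified Borg scale in Appendix 10.5 carries that word, and section 3.3.4.1 on removal of patients does not mention the rule. Second, SAP 6.6 does not say whether such a withdrawal counts as worsening of the study disease.

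After a stop at visit 6 the choice hardly matters: the visit 6 score is kept, and period 2 has no observed visit to impute from. After a stop at visit 7 it could matter. The only observed visit in period 2 is then the washout baseline. Under the worsening rule, read literally, that score would be entered at visit 9 and credited to a treatment the patient never received. At stake would be a primary-endpoint value that depends on an unwritten choice, in a trial with no allowance for attrition (Protocol 7.7).

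**Working it through.** **The plan's own figure.** Inputs from Protocol 7.7: two-sided α = 0.05, δ = 0.5, SD of the within-patient difference 1.776. For a one-sample t-test the noncentrality is (δ/SD)·√n. At n = 101 it is (0.5/1.776)·√101 = 2.83, and power is 0.8001. At n = 135 power is 0.9011. Both tabulated sizes reproduce, and n = 102 gives 0.8041.

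**If visit 9 stays missing.** Taking each affected patient as a lost pair, power is 0.800 for one patient (101 pairs), 0.792 for three (99) and 0.784 for five (97).

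**If visit 9 takes the visit 7 score.** Let d be the period 1 minus period 2 difference. The sequence-adjusted treatment effect is (mean d in AB − mean d in BA)/2, with 51 patients per sequence. Raising one period 2 value by a gap g moves it by g/(2·51) = g/102. For an assumed g of 2 to 5 Borg units:

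- 2/102 = 0.020, which is 3.9% of δ
- 5/102 = 0.049, which is 9.8% of δ

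The shift favours the combination if the patient is in AB and tiotropium if in BA. Equal numbers in each sequence cancel. Because visit 7 follows washout, there is no design reason for such stops to favour one sequence.

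**Simulation close to the planned model.** There were 1,500 trials per setting, with N = 102, true difference −0.5 and SD 1.776. Scores were rounded to 0.5 and limited to 0–10. The model was REML compound symmetry with treatment, period, period baseline and patient baseline, using a t test on 98 df in place of Kenward-Roger. Assumed, because the documents do not give them: off-treatment mean 6; tiotropium effect over washout and between-patient SD of (0.5, 2.0), (1.0, 1.5) or (1.5, 1.0); and the 1, 2 or 5 highest visit 7 scores withdrawn. Imputing compared with leaving missing:

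| Patients | Mean absolute change (Borg) | 95th percentile | Disagree on p<0.05 | Power lost by imputing |
|---|---|---|---|---|
| 1 | 0.02–0.04 | 0.03–0.06 | 2.7–7.9% | 0.5–2 points |
| 2 | 0.02–0.04 | 0.05–0.09 | 3.9–7.7% | 1–4 points |
| 5 | 0.03–0.06 | 0.08–0.16 | 5.7–13.1% | 2–8 points |

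Mean bias is at most 0.012, or 0.012/0.5 = 2.4% of δ. For scale, leaving these visits missing disagrees with hypothetical complete data on p<0.05 in 2–5% of trials.

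**What has to happen first.**

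1. A safety stop must occur at visit 7. Under Appendix 10.4.2.2 every patient has completed three minutes at the chosen speed at visit 2. The patient then repeats that speed at visit 3 and, before dosing, at visit 4.
2. The withdrawal must be recorded as worsening of the study disease. Section 3.3.4.1 requires a reason in the eCRF for every withdrawal, and section 4.1.5.1 keeps treatment blinded until after database lock. The recorded reason therefore selects the branch without knowledge of treatment.
3. The analyst must accept a six-week value for a period with no drug. Protocol 5.1.1 defines the endpoint as a change after six weeks of treatment, and SAP 6.7 ties the period baseline to dosing on day 1. SAP 6.1 also discards efficacy data from a period spent wholly on the wrong medication when the other period was correct. A plan that drops real measurements for that reason is not naturally read as creating one where no drug was taken.

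**The clinical wording.** Appendix 10.4.1 and Appendix 10.4.2 describe two kinds of stop; the connecting sentence presents the second as additional to the first. Appendix 10.4.2 leaves whether a patient can continue safely to the supervising technician or physician, and Appendix 10.4 refers to a Manual of Procedures for detail. That is a boundary left to judgement, not a contradiction. No view is taken here on where it should lie.

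**The case for a change.** The strongest reply is that the literal text does permit the bad outcome. SAP 6.6 nowhere says that a baseline is not a prior visit, and its spirometry rules, which use similar wording, name visits 4 and 7 among the visits covered. No visible rule maps the eCRF reason to a branch. Chance imbalance can also do real harm. In a simpler paired simulation (3,000 runs, stop score 9.5), three patients all in AB moved the estimate to −0.60 with power 0.90. Three all in BA gave −0.39 and 0.52, against about −0.50 and 0.78–0.79 when left missing. With three patients and no link to sequence, all fall on one side with probability about 2 × 0.5³ = 0.25. A clarifying sentence would cost little.

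The ambiguity stands, and so does the arithmetic given those inputs. But three such patients at one visit, all coded as worsening, is an assumption with nothing in the documents behind it. Three in each sequence give −0.49, with power 0.70 against 0.78. Parts of SAP 6.6 are also redacted, so the absence of a rule cannot be confirmed.

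Nor is a general ban on baselines as a source free of cost. The flow chart shows no shuttle test at visits 5 and 8, whereas its footnote 14 and Protocol 5.2 say there is one. If there is none, the pre-dose baseline is the only score available for a patient who was dosed and then discontinued for worsening before week 6. The ban would then empty the worsening rule for the primary endpoint. That is a trade-off, not a correction.

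**Conclusion.** No change follows. This is a gap in detail that blinded analysts would fill sensibly: a period in which no study drug was taken has no result after six weeks of treatment. The harmful reading needs three conditions together, and the last runs against the endpoint definition. Even on that reading, average bias is at most 0.012 Borg units for 1 to 5 patients, and the mean absolute change is 0.02–0.06 against a planned difference of 0.5. Larger effects need several patients falling in one sequence by chance.

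These sizes rest on assumed frequencies, stop scores and treatment effects; only N, δ, SD and α come from the protocol. Which test stops lead to withdrawal is a matter for the sponsor's clinicians, and the statistical conclusion does not depend on it.
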